9 ADVERSE CLINICAL EVENT REPORTING

Throughout the course of the study, every effort should be made to remain alert to possible adverse experiences. Adverse events should be recorded using the toxicity criteria of the NCI Clinical Cooperative Groups and the Cancer Treatment Evaluation Program(Appendix C). Adverse events not listed in toxicity criteria should be rated as either mild, moderate, severe, maximal/life threatening as

Grades 1, 2, 3, 4 respectively. In the event of an adverse experience, appropriate medical intervention should be provided and if necessary, the investigational agent (Zevalin) should be discontinued.

All adverse events regardless of the relationship to the study drug(s) whether observed by the investigator or reported by the patient, will be recorded with details of the duration and intensity of each episode, the action taken with respect to test drug and the patient outcome, on an appropriate source document at the clinical site. The investigator will evaluate each adverse experience as to its relationship to the test drug and as to whether or not it was serious.

All abnormal laboratory results will be appraised by the investigator as to clinical significance. For any laboratory abnormality considered clinically significant, details should be recorded on an appropriate source document including the action taken with respect to the test drug and the patient outcome.

Adverse events occurring after the initiation of other anti-cancer therapy will not be followed, unless the therapy is initiated and the adverse event occurs within 30 days following the Zevalin drug infusion.

9.A Reporting of Serious Adverse Events to the Principal Investigator, ACC DSMB, the IRB and, if necessary, the FDA

Any serious or unexpected adverse event (including death) due to any cause whether or not related to the study drug(s) must be immediately reported to the principal investigator, ACC DSMB, the IRB and drug manufacturer. The Principal Investigator must immediately complete the SAE form and arrange to have it faxed in a timely manner to the Drug Safety and Risk Management Department of Biogen Idec Incorporated [contact]). See Appendix E for SAE form.

It is the responsibility of the Investigator-Sponsor to IMMEDIATELY REPORT ALL SERIOUS OR UNEXPECTED ADVERSE IMMEDIATELY TO THE IRB CHAIR (AS PER INSTITUTION POLICY) AND, IF APPROPRIATE, TO THE FDA BY COMPLETING AND SUBMITTING A MEDWATCH FORM (FDA FORM 3500A). The Investigator-Sponsor must promptly provide a copy of the MedWatch form to Biogen Idec at the same time it is submitted to the FDA. Completed FDA 3500A reports should be faxed to the Drug Safety and Risk Management Department of Biogen Idec Incorporated [contact]). See Appendix E for additional information and a blank copy of the MedWatch form.

Serious adverse events occurring after initiation of other anti-cancer therapy do not need to be reported, unless the therapy is initiated and the event occurs within 30 days following the infusion of the study drug or the event is felt to be related to the study drug. An exception to this is the occurrence of myelodysplastic syndrome, leukemia, or other malignancy, which should be reported immediately.

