All Grade 3 and 4 events occurring in < 5% of patients (except for those noted in Table 5) consisted of pancytopenia (1.7%), allergic reaction (1.1%), dehydration (1.1%), gastrointestinal hemorrhage (0.9%), hyperglycemia (0.9%), melena (0.9%), tumor pain (0.9%), increased alkaline phosphatase (0.6%), ascites (0.6%), constipation (0.6%), increased lactic dehydrogenase (0.6%), increased SGPT (0.6%), malaise (0.6%), apnea (0.6%), bilirubinemia (0.6%), hypoxia (0.6%), deep thrombophlebitis (0.6%), hypochromic anemia (0.3%),angioedema (0.3%),anxiety (0.3%), depression (0.3%),hypoproteinemia (0.3%), increased SGOT (0.3%), insomnia (0.3%), neck pain (0.3%), pleural effusion (0.3%), somnolence (0.3%), tachycardia (0.3%), urticaria (0.3%), anemia hemolytic (0.3%), arterial anomaly (0.3%), arrhythmia (0.3%), arthritis (0.3%), cachexia (0.3%), convulsion (0.3%), coronary artery disorder, (0.3%), easy bruisability (0.3%), lung edema (0.3%), pulmonary embolus (0.3%), encephalopathy (0.3%), granulocytosis (0.3%), congestive heart failure (0.3%), hematemesis (0.3%),

subdural hematoma (0.3%), hepatic failure (0.3%), hypercalcemia (0.3%), hyperuricemia, (0.3%), increased prothrombin (0.3%), myocardial ischemia (0.3%), jaundice (0.3%), kidney failure (0.3%), migraine (0.3%), neuritis (0.3%), intestinal obstruction (0.3%), eye pain (0.3%), respiratory disorder (0.3%), supraventricular tachycardia (0.3%), vaginal hemorrhage (0.3%), and increased venous pressure (0.3%).

Hematologic Events: Hematologic toxicity has been frequently observed in clinical trials, and is dose-limiting. Table 6 presents the incidence and duration of Grade 3 and 4 hematologic toxicity for patients with mild thrombocytopenia at baseline who were treated at 0.3 mCi/kg (11.1 MBq/kg), and for those with normal baseline platelet count treated at 0.4 mCi/kg (14.8 MBq/kg), up to the maximum dose of 32 mCi (1184 MBq).

Table 6 Hematologic Toxicity

	Median Nadir	Patients with Grade 3 Toxicity	Patients with Grade 4 Toxicity	Days Within Grade 3 or 4* (Median for all Patients)	Days Within Grade 3 or 4* (Median for Patients with Grade 3 or 4 Nadir)	
0.3 mCi/kg; 11.1 MBq/kg dose (maximum 32 mCi; 1184 MBq)						
ANC (cells/mm ³)	600	40%	35%	23.0	29.0	
Platelets (/mm³)	24,000	66%	14%	29.0	34.5	
Hemoglobin (g/dL)	10.0	12%	8%	0.0	14.0	
0.4 mCi/kg; 14.8 MBq	/kg dose (m	aximum 32 m	Ci; 1184 MB	q)		
ANC (cells/mm³)	800	28%	30%	14.0	22.0	
Platelets (/mm ³)	41,000	52%	10%	15.0	24.0	

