An adverse event (AE) is any untoward medical occurrence in a patient or clinical investigation subject administered a pharmaceutical product and that does not necessarily have a casual relationship with this treatment. An AE can therefore be any unfavorable and unintended sign, symptom, or disease temporally associated with the use of a medicinal (investigational) product, whether or not related to the medicinal (investigational) product.

Any and all adverse events will be recorded on the UMC adverse events record form and reviewed by the Principal Investigator.

All adverse events will be classified using either the MedDRA term or NCI Common Terminology Criteria for Adverse Events (CTCAE) version 3.0 and will address:

- Grade
- Relationship to study drug(not related, unlikely, possible, probable, definitely)
- Causality other than study drug (disease related, concomitant medication related, intercurrent illness, other)
- Date of onset, date of resolution
- Frequency of event (single, intermittent, continuous)
- Event outcome (resolved, ongoing, death)
- Action taken (none, held, dose reduced, discontinued, medication given)

SERIOUS ADVERSE EVENTS

A serious adverse event (SAE) is any untoward medical occurrence that at any dose:

- 1) Results in death;
- 2) Is life-threatening;
- 3) Requires in-patient hospitalization or prolongation of an existing hospital stay;
- 4) Results in disability persistent or significant disability/incapacity, or:
- 5) Is a congenital anomaly/birth defect.

Note: A SAE may also be an important medical event, in the view of the investigator that requires medical or surgical intervention to prevent one of the outcomes listed above.

All serious adverse events, regardless of attribution, and any deaths will be reported within 24 hours of notification of the event to the sponsor and DSMB Coordinator. All serious adverse events, regardless of attribution, and any deaths will be reported within 5 days of notification of the event to the University of Arizona Human Subjects Protection Program.

All serious adverse events will be processed by the DSMB Coordinator monthly for initial trend analysis and fully reviewed by the DSMB, every six months. The DSMB coordinator will review the SAE reporting process to confirm reporting requirements are met.

6. Plan for assuring data accuracy and protocol compliance:

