APPENDIX C

ADULT TOXICITY CRITERIA (CTC)

Common Terminology Criteria for Adverse Events v3.0 (CTCAE)

Publish Date: August 9, 2006

Quick Reference

The NCI Common Terminology Criteria for Adverse Events v3.0 is a descriptive terminology which can be utilized for Adverse Event (AE) reporting. A grading (severity) scale is provided for each AE term.

Components and Organization

CATEGORY

A CATEGORY is a broad classification of AEs based on anatomy and/or pathophysiology. Within each CATEGORY, AEs are listed accompanied by their descriptions of severity (Grade).

Adverse Event Terms

An AE is any unfavorable and unintended sign (including an abnormal laboratory finding), symptom, or disease temporally associated with the use of a medical treatment or procedure that may or may *not* be considered related to the medical treatment or procedure. An AE is a term that is a unique representation of a specific event used for medical documentation and scientific analyses. Each AE term is mapped to a MedDRA term and code. AEs are listed alphabetically within CATEGORIES.

Short AE Name

The 'SHORT NAME' column is new and it is used to simplify documentation of AE names on Case Report Forms.

Supra-ordinate Terms

A supra-ordinate term is located within a CATEGORY and is a grouping term based on disease process, signs, symptoms, or diagnosis. A supra-ordinate term is followed by the word 'Select' and is accompanied by specific AEs that are all related to the supra-ordinate term. Supra-ordinate terms provide clustering and consistent representation of Grade for related AEs. Supra-ordinate terms are not AEs, are not mapped to a MedDRA term and code, cannot be graded and cannot be used for reporting.

REMARK

A 'REMARK' is a clarification of an AE.

ALSO CONSIDER

An 'ALSO CONSIDER' indicates additional AEs that are to be graded if they are clinically significant.

NAVIGATION NOTE

A 'NAVIGATION NOTE' indicates the location of an AE term within the CTCAE document. It lists signs/symptoms alphabetically and the CTCAE term will appear in the same CATEGORY unless the 'NAVIGATION NOTE' states differently.

Grades

Grade refers to the severity of the AE. The CTCAE v3.0 displays Grades 1 through 5 with unique clinical descriptions of severity for each AE based on this general guideline:

Grade 1 Mild AE

Grade 2 Moderate AE

Grade 3 Severe AE

Grade 4 Life-threatening or disabling AE

Grade 5 Death related to AE

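### Section 9 asks for details of laboratory abnormalities judged clinically significant, Appendix C's adverse event definition has no such filter, and the recorded cytopenia frequency would depend partly on judgement

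*Combined protocol and SAP*

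**What the plan says.** Section 9 (Adverse Clinical Event Reporting) holds two recording rules.

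- **General rule.** Adverse events are recorded with the Appendix C toxicity criteria. Every event, whatever its relationship to treatment, goes on a source document with its duration, intensity, action taken and outcome.
- **Laboratory rule.** "All abnormal laboratory results will be appraised by the investigator as to clinical significance". The next sentence reads: "For any laboratory abnormality considered clinically significant, details should be recorded on an appropriate source document", again with action taken and outcome. Clinical significance is not defined and no threshold is given.

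Appendix C (CTCAE v3.0) has no significance step: "An AE is any unfavorable and unintended sign (including an abnormal laboratory finding), symptom, or disease temporally associated" with a medical treatment or procedure. Section 13.E, item 5, says: "Any and all adverse events will be recorded on the UMC adverse events record form", and asks for a grade. Its own definition covers unfavorable and unintended signs but does not name laboratory findings.

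Section 12.A gives safety of the ESHAP-Zevalin combination as an aim beside efficacy. Section 6.C.6 says of earlier Zevalin trials: "Hematologic toxicity has been frequently observed in clinical trials, and is dose-limiting". Section 12.C plans PFS, response rates and a Kaplan-Meier curve, and no toxicity summary. Under Section 13.E, item 6, the six-monthly DSMB report carries a safety narrative and the adverse event data reviewed by the principal investigator.

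**The concern.** Cytopenia after ESHAP or 90Y Zevalin is expected and often silent, so it is the finding most likely to be judged not clinically significant. Two people following the protocol could treat the same asymptomatic Grade 3 platelet count differently. One leaves it off under Section 9's laboratory rule. The other records and grades it under Appendix C and Section 13.E.

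What is at stake is the safety description. No analysis plan commits the sponsor to summarising haematologic toxicity from the counts, so the adverse event record is the documented source for the DSMB and probably for any report. If judgement decides what enters it, a low recorded frequency could mean little toxicity or a strict view of significance, and a reader could not tell which.

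**Working it through.** **1. The plan's own number.** The point rests on no planned figure. The design figure was checked to confirm that nothing here touches it. With p0 = 0.50, p1 = 0.673, one-sided alpha 0.10 and power 0.90 (z = 1.2816 for both):

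n = [1.2816 × (√(0.50 × 0.50) + √(0.673 × 0.327)) / (0.673 − 0.50)]² = [1.2816 × (0.5000 + 0.4691) / 0.173]² = 51.5, rounded up to 52.

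This reproduces Section 12.B, and no laboratory recording rule enters it.

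**2. The rules side by side, for an asymptomatic Grade 3 platelet count after 90Y Zevalin.**

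| Place | Test for recording | Result |
|---|---|---|
| Section 9, laboratory rule | Considered clinically significant by the investigator | Recorded or not, by judgement |
| Appendix C, adopted by Section 9 | Unfavorable, unintended, temporally associated; laboratory findings included | Adverse event, graded |
| Section 13.E, item 5 | All adverse events | Recorded, if Appendix C's definition is used |

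No sentence ranks these rules.

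**3. Are objective data available?** Yes, in part. CBCs are scheduled at baseline, Cycle 2 Day 1, Cycle 2 Day 29, within 28 days before rituximab and Zevalin, weekly from Day 35 (± 7 days) until past nadir, at restaging, at follow-up and off study (Section 5, Appendix A). The Table 6 footnote gives numeric Grade 3 or 4 limits: ANC below 1,000/mm³, platelets below 50,000/mm³, hemoglobin below 8.0 g/dL. A count-based rate could therefore be derived, but the plan does not say that it will be. Section 13.E names eligibility, adverse event and serious adverse event forms. It names no laboratory form, though it leaves other forms open.

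**4. Illustration of size.** Assumptions: the Zevalin-alone rates in Table 6 apply here; each patient is counted once, at worst grade; the share f of Grade 3-4 events that gets recorded runs from 50% to 100%. The documents give no value for f. Recorded rate = f × (Grade 3 % + Grade 4 %).

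| Dose group, Table 6 | Grade 3 + Grade 4 | f = 100% | f = 75% | f = 50% |
|---|---|---|---|---|
| 0.4 mCi/kg, platelets | 52 + 10 | 62% | 46.5% | 31% |
| 0.4 mCi/kg, ANC | 28 + 30 | 58% | 43.5% | 29% |
| 0.3 mCi/kg, platelets | 66 + 14 | 80% | 60% | 40% |
| 0.3 mCi/kg, ANC | 40 + 35 | 75% | 56.25% | 37.5% |

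The spread arises only if the rate is taken from the adverse event record and not from the CBC values.

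**The case against.** The best defence is that the laboratory sentence adds to the general rule and does not restrict it: Section 9 already has all adverse events recorded by Appendix C, and merely wants extra detail for significant laboratory results. It is true that the sentence does not exclude other results in so many words. But the general rule already asks for details, action taken and outcome on a source document. If an abnormal count were already covered there, the laboratory sentence would add nothing. It reads more naturally as a separate, filtered rule, and at best it is ambiguous.

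The second defence is that scheduled counts and numeric cut-offs make an objective rate recoverable. That stands. It limits the harm and makes the fix cheap, but it does not supply the missing commitment.

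Several stronger readings are tempting and are not supported:

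- **That an abnormality is recorded only when judged significant.** This is an inference, since Section 9 also requires all adverse events.
- **That Appendix C makes every abnormal value an adverse event.** The finding must be unfavorable, unintended and temporally associated.
- **That a dose-limiting cytopenia rate is compromised.** The plan defines none; the phrase in Section 6.C.6 describes earlier trials. Nor is Table 6 named as a comparator. The stated historical comparisons are of TTP and OS (Section 1.E) and 1-year PFS (Section 12.A).
- **That the same counts could appear as about 5 or 32 patients with severe thrombocytopenia** (0.10 × 52 = 5.2; 0.62 × 52 = 32.2). This needs every Grade 3 event to be dismissed and all 52 patients to reach 90Y. The documents support neither: Sections 3.A and 7.B.2 provide for patients who stop before it.
- **That ESHAP toxicity is lost through attribution.** Section 9 speaks of "the investigational agent (Zevalin) should be discontinued" and then says: "The investigator will evaluate each adverse experience as to its relationship to the test drug". But it also refers to study drugs in the plural form and records events whatever the relationship, so attribution removes none. This is a matter of clarity.

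**Conclusion.** The conflict is real and in current text. As written, an asymptomatic Grade 3-4 cytopenia could be left off the adverse event record under one rule and belongs on it under another, so the recorded frequency would depend partly on judgement.

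The extent cannot be derived, because the documents do not give the share of events that investigators would call significant. The ranges of 31% to 62% for platelets and 29% to 58% for ANC at 0.4 mCi/kg are illustrations under assumed shares and Zevalin-alone rates, and do not predict this trial's results. The primary endpoint, alpha, power and the 52 patients are untouched. This is a weakness in safety recording, worth correcting because safety is a stated aim and the remedy is small.

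**What to change.** Reconcile Section 9 with Appendix C by stating that:

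1. the CBC and creatinine values already collected are graded by CTCAE v3.0 from the reported value;
2. worst grade per patient is derived from those values separately for the ESHAP and Zevalin phases, with the dates of each phase defined;
3. clinical significance is a separate field that does not decide whether a value is recorded.

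It would also help to name the haematologic summary in Section 12.C and say that it comes from graded values.

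The cost is protocol and CRF wording and a short grading program, with no new tests. There will be more adverse event rows and possibly a higher reported toxicity rate. Nadirs between scheduled CBCs would still be missed. For example, Section 6.A.1 puts the high-dose cisplatin nadir at about two weeks, whereas the next scheduled count after Cycle 1 Day 1 is at Cycle 2 Day 1, 28 days later. The summary should state that limit.

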3 STUDY DESIGN

3.A Treatment Summary

After informed consent has been obtained, patients will undergo screening to assure eligibility for the study. After two cycles of ESHAP have been given, patients will be restaged to determine response. Patients with residual involvement of more than 25% of bone marrow after the two cycles of ESHAP will be taken off treatment and followed for time to progression and survival. Patients experiencing disease stabilization or reduction with less than 25% residual bone marrow involvement will undergo imaging for biodistribution. If biodistribution is acceptable, then patients will receive the Zevalin treatment and undergo a second disease evaluation for response assessment. Thereafter, patients will be followed at 6 month intervals (Short-term follow-up) for 2 years, and then annually (Long-Term follow-up) for an additional 3 years

3.B Study Duration

The estimated active accrual period for this study is 5 years. After completion of treatment, patients will be followed for 5 years to allow determination of study endpoints.

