For the purpose of toxicity assessment, the treatment period will include the time from the first ESHAP infusion to 30 days following Zevalin infusion. Evaluations during the 2 cycles of ESHAP are outlined in Appendix A.

5.B.1 ESHAP Cycle 1, Day 1

a. Begin ESHAP Treatment (Please refer to Section 7A for ESHAP administration)

5.B.2 ESHAP Cycle 2, Day 1

- a. History & Physical examination, including vital signs (BP, temperature & pulse), height, weight, Body Surface Area (BSA), and performance status (Appendix B).
- b. Laboratory tests including:
 - Complete blood count (CBC) with differential and platelet count
 - Serum chemistries BUN, creatinine
- c. Toxicity Assessment: Adverse events are to be recorded on an ongoing basis and on appropriate source documents at the clinical site and in the patient's case report form.

5.B.3 ESHAP Cycle 2, Day 29

- a. History & Physical examination, including vital signs (BP, temperature & pulse), height, weight, Body Surface Area (BSA) & performance status (Appendix B).
- b. Laboratory tests including:
 - Complete blood count (CBC) with differential and platelet count
 - Serum chemistries BUN, creatinine
- c. Unilateral or Bi-lateral bone marrow biopsy and aspirate for histology and determination of percent bone marrow involvement
- d. Bone marrow cytogenetics. Does not have to be done at each Bone Marrow biopsy and aspirate, but does need to be completed at either, Baseline or Cycle 2, Day 29.
- e. Disease Assessment:
 - Total of all measurable indicator lesions.
 - CT or PET scan of the chest, abdomen and pelvis
- f. Toxicity Assessment: Adverse events are to be recorded on an ongoing basis and on appropriate source documents at the clinical site and in the patient's case report form.

5.C Evaluations During the Zevalin Imaging & Treatment Period

Ibritumomab Tiuxetan Indium (111 In Zevalin) regimen is administered 4 – 6 weeks after completion of ESHAP.

5.C.1 Day 1

- a. History & Physical examination, including vital signs (BP, temperature & pulse), height, weight, Body Surface Area (BSA), and performance status are to be performed within 28 days of Rituximab & Zevalin administration. (Appendix B).
- b. Toxicity Assessment: Adverse events are to be recorded on an ongoing basis and on appropriate source documents at the clinical site and in the patient's case report form.
- c. Laboratory tests including:
 - Complete blood count (CBC) with differential and platelet count
 - Serum chemistries BUN, creatinine

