5.F.1 Tests to be Performed When a Patient is Determined to Have Disease Progression or is Removed from the Study for any Reason

The following tests will be performed within 4 weeks after a patient has demonstrated progression of disease, or removed from study:

It is strictly mandated that patients not be given other myelosuppressive anti-neoplastic agents until recovery from hematologic nadir.

These tests do not have to be repeated if they were performed within 7 days prior to documentation of disease progression.

- a. History & Physical examination, including vital signs (BP, temperature & pulse), height, weight, Body Surface Area (BSA), and performance status (Appendix B).
- b. Laboratory tests including:
 - Complete blood count (CBC) with differential and platelet count
 - Serum chemistries BUN, creatinine

• LDH

c.Disease Assessment (if patient is removed from the study for a cause other than progressive disease):

- Total of all measurable indicator lesions.
- CT or PET scan of the chest, abdomen and pelvis

d.Toxicity Assessment: Adverse Events (AE) are to be recorded on an ongoing basis until resolved or determined to be permanent. All AEs are to be documented on appropriate source documents at the clinical site and in the patient's case report form.

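### Patients who receive ESHAP but never Zevalin have no safety window for new adverse events once other therapy starts, and Sections 9.A and 13.E disagree on which late serious events and deaths are reported

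*Combined protocol and SAP*

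**What the plan says.** Section 9 sets the general cut-off: "Adverse events occurring after the initiation of other anti-cancer therapy will not be followed". The single exception requires that both the start of the new therapy and the event fall "within 30 days following the Zevalin drug infusion". Section 5.B uses the same anchor for toxicity assessment: "the treatment period will include the time from the first ESHAP infusion to 30 days following Zevalin infusion".

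The protocol plans for patients who will not reach Zevalin. Under 3.A, "Patients with residual involvement of more than 25% of bone marrow after the two cycles of ESHAP will be taken off treatment". The note to 4.A.12 adds platelet, creatinine and bilirubin conditions for going on to Zevalin, and 7.B.2 takes patients with altered biodistribution off study before the 90Y dose. Under 4.C and 12.B, one dose of ESHAP makes a patient evaluable.

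Section 5.F provides 30 days of safety follow-up after treatment is discontinued, but only for patients who progress during the treatment period and have not begun other anti-cancer therapy. For patients off study for any reason, 5.F.1.d says "Adverse Events (AE) are to be recorded on an ongoing basis until resolved or determined to be permanent" and does not mention new therapy.

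On serious events, 9.A opens by requiring immediate reporting of any serious or unexpected event, death included, whatever the cause. It then states "Serious adverse events occurring after initiation of other anti-cancer therapy do not need to be reported", apart from events within 30 days of the study drug infusion, events felt to be related to it, and myelodysplastic syndrome, leukemia or other malignancy. Section 13.E says "All serious adverse events, regardless of attribution, and any deaths will be reported within 24 hours of notification of the event", with no such exemption. For the IRB, 9.A says immediately and 13.E says within 5 days.

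**The concern.** Section 12.A presents the trial as one of both efficacy and safety of the ESHAP-Zevalin sequence, and the evaluable population starts at the first ESHAP dose. If the period for capturing new events depends on whether Zevalin was given, ascertainment is unequal inside that population, and the inequality follows from how the patient fared on ESHAP. An event missed in this way can only lower the recorded toxicity of the ESHAP phase.

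The second issue is about oversight. Under 13.E the DSMB reviews serious adverse events every six months. If two sections of one protocol set different reporting duties for the same late death, what the board sees depends on which section the site applied.

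**Working it through.** The plan states no figure to reproduce. The check compares the windows and then the reporting rules.

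**1. Window for new events after other therapy starts (Section 9).** Let d be the number of days from the anchoring infusion to the start of other therapy.
- Zevalin given: remaining window = 30 − d days when d is below 30. For example, d = 10 leaves 20 days.
- Zevalin never given: there is no anchoring infusion, so the exception cannot apply and the remaining window is 0 days.

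**2. Does another section fill the gap?**
- 5.B: its period closes 30 days after Zevalin, so without Zevalin it has no stated end.
- 5.F: its 30 days excludes anyone who begins other therapy, which is the situation in question.
- 3.A: patients stopped for marrow involvement are followed for progression and survival; safety is not mentioned.
- 5.F.1.d: this keeps toxicity already present under observation. Whether it also reaches events that begin after new therapy is not stated; if it does, it contradicts Section 9.

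The gap is therefore confined to new-onset events.

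**3. Days lost by patients stopped on schedule.** Inputs: ESHAP on Days 1–4 of a 28-day cycle (Table 7); restaging at Cycle 2 Day 29 (5.B.3).
- Last dose to restaging: 29 − 4 = 25 days.
- A 30-day window from the last dose ends on Day 4 + 30 = Day 34.
- Loss if other therapy starts on Day 29 itself: 34 − 29 = 5 days.
- A patient stopped when Cycle 2 is due on schedule is also 28 + 1 − 4 = 25 days past the Cycle 1 Day 4 dose: again 5 days. If Cycle 2 has been put off by a week, 25 + 7 = 32 days have passed and nothing is lost.

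A longer loss needs three things together: stopping between these assessments, starting other therapy within 30 days of the last ESHAP dose, and then having a new event.

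**4. Patients stopped for altered biodistribution.** They have had rituximab and the 111In dose. The text does not say whether that imaging dose counts as the Zevalin infusion in Section 9. If it does, a patient stopped after the 48–72 hour scan has 30 − 3 = 27 to 30 − 2 = 28 days left; if not, none.

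**5. Serious events after other therapy has started.**

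| Event | 9.A | 13.E |
|---|---|---|
| Therapy started and event occurred within 30 days of the study drug infusion | report | report |
| Later, felt related to study drug | report | report |
| Myelodysplastic syndrome, leukemia, other malignancy | report | report if serious |
| Later, serious or fatal, not felt related | exempt | report within 24 hours |

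The last row is the conflict. The first row is also unclear for ESHAP-only patients, because Section 9 calls Zevalin the investigational agent yet elsewhere allows for more than one study drug. If only Zevalin counts, the 30-day exception in 9.A is closed to them as well.

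**The case against.** The strongest case on the other side is that little is lost. Toxicity present when other therapy starts stays on record under 5.F.1.d, and 5.F.1 requires examination, blood counts, renal chemistry and toxicity assessment within 4 weeks of removal. On-schedule patients lose at most 5 days. Sections 5.F.1 and 10 forbid other myelosuppressive drugs until recovery from the nadir, which limits early switching. Stopping capture at the next therapy also keeps that therapy's effects out of the data. Section 2 lists no safety objective, and 12.C commits only to progression-free survival, response and time to progression, so no planned safety estimate can be shown to be biased. All of this stands and limits the size of the point. It does not supply a window for patients who never receive Zevalin.

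On serious events, the 9.A wording is permissive, so a site that follows 13.E breaches neither section. Section 8.C also sends unexpected or fatal toxicities to the DSMB, and 13.C calls for forms at death. That is fair, but a site relying on 9.A would still miss a 13.E duty for an unrelated late death.

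A reader might infer more than the documents support:
- **That all adverse-event follow-up ends when new therapy begins.** Section 9 concerns events that occur after that point.
- **That a known number of patients is affected.** Assuming 10–25% of 52 never receive Zevalin gives 0.10 × 52 = 5.2 to 0.25 × 52 = 13, but no rate is stated, and this counts everyone without Zevalin rather than those meeting all three conditions in step 3.
- **That patients typically leave follow-up before the nadir.** The nadir timings in Section 6.A are for 5–7 days of etoposide and for high-dose cisplatin, not for this 4-day regimen.
- **That patients who fail ESHAP are the frailest.** The documents do not say so.

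**Conclusion.** The point holds within limits. On the current text, ESHAP-only patients have no window for adverse events that begin after other therapy starts, and 5.B and 5.F do not provide one. The cost is about 5 days for patients stopped on schedule at Cycle 2 Day 29 and is potentially longer for those who stop earlier and switch within 30 days. Because the documents give no number of such patients, the effect on the recorded toxicity cannot be computed; only its direction, under-recording, can be stated. The 5-day figure assumes that ESHAP is given on the Table 7 schedule and that other therapy starts on Day 29.

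The inconsistency between 9.A and 13.E is established by the text alone. It covers serious events and deaths after new therapy that are beyond 30 days, not felt related and not a second malignancy, and it extends to the IRB timeline. Neither issue threatens the primary endpoint. Both deserve correction because safety is a stated purpose and the remedy is inexpensive.

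**What to change.** - In 5.B, 5.F, 9 and 9.A, count the 30-day safety window from the last dose of any protocol treatment (ESHAP, rituximab, 111In or 90Y Zevalin), whether or not other anti-cancer therapy has begun. This also settles the status of the imaging dose and of the term study drug.
- Reconcile 5.F.1.d with Section 9, stating separately how long existing events are followed and until when new events are collected.
- Merge the serious-event and death rules of 9.A and 13.E into one rule that says explicitly whether the exemption after new therapy applies and gives one IRB timeline. Have the other section refer to it.
- State in 12.C that toxicity is reported for all ESHAP-treated patients over this window.

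The cost is a wording amendment plus, for patients who stop early, adverse-event recording for at most 30 days after their last protocol dose. The downside is small: some events caused by the next therapy will be captured and will need attribution, which the 13.E form already asks for.
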